3.5.1 Adverse Events (AEs)

AEs will be categorized by primary system organ class and preferred term as coded using the current MedDRA version category designation.

An overview of treatment-emergent AEs (TEAEs) will be provided including counts and percentages of participants with the following:

- Any TEAEs (overall and by maximum severity)
- Any TEAEs (non-serious)
- Any study drug related TEAEs (overall and by maximum severity)
- Any TEAEs leading to discontinuation of study drug
- Any treatment-emergent serious AEs (TESAEs)

- Any study drug related TESAEs
- Any TEAEs leading to death.

The TEAEs described above will be summarized separately by system organ class and preferred term. The non-serious TEAEs occurring in more than 2% of participants in any treatment group and preferred term will be summarized.

Listings will be presented specifically for TEAES, TESAEs, TEAEs leading to discontinuation of study drug and TEAEs leading to death.

3.5.2 Event of Special Interest

Events of special interest (ESIs) include the following: hepatic abnormalities, muscle-related abnormalities, new-onset diabetes mellitus (NODM) and/or hyperglycemia, renal abnormalities, changes to antihypertensive medication(s) due to changes in blood pressure, and macular degeneration described as follows:

- AST or ALT > 3×ULN;
- Total bilirubin > 2×ULN;
- Creatine kinase (CK) > 5 × ULN;
- NODM or worsening of glycemic control;

Note: NODM is defined by 1 or more of the following criteria, based upon information from AE, medication, and laboratory data:

- AE indicating new type 1 or type 2 diabetes;
- Initiation of anti-diabetes medication with confirmation of the diagnosis of diabetes by blinded external review by experts in diabetology;
- HbA1c ≥6.5% (≥ 0.065 hemoglobin fraction); and/or
- Two consecutive values of fasting plasma glucose that are ≥ 126 mg/dL ($\geq \text{mmol/L}$).

Note: Worsening of glycemic control will be defined as HbA1c increase from Baseline $>0.5\%$ (>0.005 hemoglobin fraction) and/or a new concomitant medication or increase in current antidiabetic therapy in a participant with a Baseline HbA1c $\geq 6.5\%$ (≥ 0.065 hemoglobin fraction)

- A $>25\%$ decrease in eGFR from Baseline or an eGFR $<30\text{mL/min}/1.73\text{ m}^2$, calculated using the Chronic Kidney Disease Epidemiology Collaboration equation, and/or an increase in serum creatinine of ≥ 0.3 mg/dL ($\geq 26.5\text{ }\mu\text{mol/L}$) from Baseline;
- Changes to antihypertensive medication(s) due to changes in blood pressure in those participants receiving antihypertensive medication(s) treatment at Baseline and those participants not receiving antihypertensive medication(s) treatment at Baseline; and
- Macular degeneration.

An overview of ESIs described above will be provided including counts and percentages of participants by treatment group, and a listing of each ESI.

Values and changes from baseline will be summarized for ALT, AST, and total bilirubin by visit and treatment group. The number and percent of participants with abnormal values for ALT, AST, and total bilirubin will be summarized. These summaries of participants with abnormal values will be performed overall; by normal Baseline; and by abnormal Baseline for ALT, AST, and total bilirubin individually. Hy's Law criteria ($>3 \times \text{ULN}$ for either ALT or AST, with accompanying total

bilirubin $>2 \times$ ULN) will also be applied to the data. Any potential Hy's Law cases will be listed separately.

Muscle-related abnormalities will be summarized by treatment group and by Baseline eGFR category.

Values and changes from baseline will be summarized for CK levels by visit and treatment group and visit. In addition, the number and percent of participants with abnormal CK values will be summarized. These summaries of participants with abnormal CK values will be performed overall, by normal Baseline CK, and by abnormal Baseline CK. Values of CK from Baseline to EOT will be summarized by treatment group and by Baseline eGFR category.

Cases of NODM will be recorded and summarized using the appropriate system organ class. These events will be summarized by severity and relationship to study drug for each treatment group. Fasting plasma glucose and HbA1c will be monitored as specified in [Table 1 Schedule of Procedures](#).

Baseline eGFR will be summarized by treatment group for actual value and for Baseline eGFR categories. Shift tables of eGFR category from Baseline to EOT will be provided by treatment group. Shift tables of urine albumin-creatinine ratio and urine protein-creatinine ratio from Baseline to EOT will be provided by treatment group.

Participants will be identified who had a diagnosis of hypertension in their medical history and received antihypertensive medication(s) at Baseline. If participants had an adverse event related to hypertension after Baseline (see [Appendix B](#) for preferred terms) and had any change in antihypertension medication within 30 days of the start date of the adverse event, that change in antihypertension medication will be considered as due to a change in blood pressure.

Participants will be identified who did not have a prior diagnosis of hypertension in their medical history and did not receive antihypertensive medication(s) at Baseline. If participants had an adverse event of hypertension and had initiation of antihypertension medication within 30 days of the start date of the adverse event, that initiation of an antihypertension medication will be considered as due to a change in blood pressure.

The number and percentage of participants receiving/not receiving antihypertensive medication(s) at Baseline with changes to or initiation of new antihypertensive medication(s) due to changes in blood pressure will be summarized by treatment group.

Cases of macular degeneration will be recorded and summarized using the appropriate system organ class. These events will be summarized by severity and relationship to study drug for each treatment group.

3.5.3 *Clinical Laboratory Tests*

Blood and urine samples for clinical laboratory evaluations (including a full serum chemistry panel, hematology, coagulation, and urine dipstick analysis) will be collected at visits specified in Table 1. Only urine dipstick analysis will be performed locally, while the rest of clinical laboratory test will be processed by a central laboratory. See Appendix A of the protocol for a complete list of analytes. Blood samples (a full serum chemistry panel, hematology, coagulation) must be collected under fasting conditions (a minimum of 8 hours) and prior to the next dose of study drug (at applicable visits).

Laboratory values will be summarized descriptively, including the change from baseline. In addition, shift tables for select parameters will be presented to describe the change in laboratory parameter values at post-baseline visits using normal range categories (low, normal, and high).

Chemistry and hematology laboratory parameters will be listed.

3.5.4 *Vital Signs*

Vital signs (heart rate and blood pressure) measured in triplicate prior to study administration at applicable visits as indicated in [Table 1](#). Values will be summarized with descriptive statistics, including the change from baseline at each visit by treatment group and overall.

Additional summaries of blood pressure measurements will be performed, within treatment group and time point, using counts of triplicate means that meet the following criteria:

- Systolic blood pressure:
 - ≥ 160 mmHg
 - ≥ 180 mmHg
 - change from baseline by ≥ 20 mmHg
- Diastolic blood pressure:
 - ≥ 100 mmHg
 - ≥ 110 mmHg
 - change from baseline by ≥ 15 mmHg.

Vital signs will be listed.

3.5.5 *Electrocardiograms*

A single 12-lead ECG will be performed at Visit 2 and Visit 7/EOT/ET and will be read locally.

ECG parameters will be recorded as normal, abnormal or not done. Abnormal values will be assessed as clinically significant or not clinically significant. Counts and percentages for ECG parameters will be summarized by treatment group and in total.

3.5.6 *Physical Examinations*

Physical examinations (with focused examination on general, respiratory, CV, abdominal, and extremities evaluations; ophthalmological examination; and recording of weight and height will be performed at Screening Visit and Visit 7/EOT/ET. Height will be measured at Screening Visit only and used to calculate body mass index. BMI will be calculated as weight/(height/100)² (kg/m²); rounded and displayed to 1 decimal place.

Physical examination parameters will be recorded as normal, abnormal or not done. Abnormal values will be assessed as clinically significant or not clinically significant. Count and percentages for physical parameters will be summarized by treatment group and in total.

Physical examination will be listed.

3.5.7 *24-hour ABPM*

Participants who consent to participate in the ABPM substudy will have a 24-hour ABPM assessment conducted at Screening (Visit 1, Baseline) and at Day 270 (Visit 6). If necessary, a repeated assessment can be completed within the respective visit window and performed such that the assessment is not done concurrently with other study procedures.

Blood pressure and heart rate measurements will be obtained every 20 minutes during the interval of 06:00 hours to 21:59:59 hours (daytime period), and every 30 minutes during the interval of 22:00:00 hours to 05:59:59 hours (nighttime period). Within a 24-hour recording, 64 measurements would be expected (16 hours of 3 recordings/hour and 8-hours of 2 recordings/hour). A valid ABPM will have no more than 2 consecutive hours without a measured and recorded blood pressure reading and have at least 70% (≥ 45 recordings) of the overall readings with a measured and recorded blood pressure reading.

Counts and percentage of participants with non-missing blood pressure measurements will be presented by time, visit and treatment group.

Descriptive statistics for 24-hour average systolic blood pressure (SBP), diastolic blood pressure (DBP) and heart rate values, including the change from baseline, will be presented at each visit by treatment groups and overall. Additionally, hourly average summaries of diastolic and systolic blood pressure will be provided by visit and treatment group.

Summaries of blood pressure measurements that meet the following criteria will be performed by time daytime period average, and nighttime average, visit and treatment group:

- Systolic blood pressure:
 - ≥ 160 mmHg
 - ≥ 180 mmHg
 - change from baseline by ≥ 20 mmHg
- Diastolic blood pressure:
 - ≥ 100 mmHg
 - ≥ 110 mmHg
 - change from baseline by ≥ 15 mmHg.

The change in average 24-hour SBP from Baseline to Day 270 will be analyzed using an ANCOVA model with a fixed effect for the treatment group and covariates of Baseline average SBP, Age, Sex and background diagnosis of hypertension. The change in average 24-hour SBP from Baseline to Day 270 will be presented by treatment group with a 2-sided 95% CI (1-sided $\alpha = 0.025$) for the difference between the treatment groups. Obicetrapib will be considered non-inferior to placebo if the upper bound of the 2-sided 95% CI (1-sided $\alpha = 0.025$) for the difference between the treatment groups is less than the non-inferiority margin corresponding to 3 mmHg.

The model will be fit assuming unequal variances for each treatment group. The primary analysis will be conducted based on the 24-hour ABPM Population.

A sensitivity analysis will be performed using all randomized participants from ITT Population who received at least 1 dose of study drug and had either a Baseline or Day 270 ABPM assessment. If the participant only had an assessment at one of these two visits, the value at the missing visit will be imputed. Similarly, if a participant had an invalid ABPM assessment (following the definition of a valid ABPM assessment described previously), the records at that visit will be set to missing and the overall assessment value will be imputed. Missing data will be imputed based on multiple imputation methodology assuming the data are MAR. The variables for the imputation model will consist of the SBP values from Baseline and Day 270, along with treatment group, Age, Sex and background diagnosis of hypertension. For the imputation methodology, 100 imputed data sets will be generated with no missing values at Day 270. For each imputation data set, the change from baseline to Day 270 will be analyzed using the ANCOVA model described above. The results of these 100 analyses will be combined to construct the treatment estimates using the parameter

estimates and associated standard errors. Similarly, the difference of the adjusted treatment means (obicetrapib vs. placebo) will be presented with the associated standard error and two-sided 95% confidence interval. Randomly chosen seed numbers will be selected for the analysis and will be retained. The sample SAS code can be found in [Appendix D](#).

A supplemental analysis will be performed consisting of participants in the 24-hour ABPM Population who did not discontinue study drug prior to the Day 270 assessment. The change in average 24-hour SBP from Baseline to Day 270 will be analyzed using a similar ANCOVA model as the primary ABPM assessment.

Similar ANCOVA models as described for SBP will be used to assess the change from Baseline to Day 270 in average SBP daytime period and average SPB nighttime period in the obicetrapib group compared to the placebo group.

Forest plots of daytime period, nighttime period, and 24-hour change from Baseline with 95% confidence interval will be displayed for SBP.

The change in average 24-hour DBP from Baseline to Day 270 will be analyzed using similar methods as for SBP.

24-hour ABPM data will be presented in participants listing.

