- 4. Are on maximally tolerated lipid-modifying therapy as an adjunct to a lipid-lowering diet and other lifestyle modifications, defined as follows:
  - o A statin at a maximally tolerated stable dose;
    - A participant's maximally tolerated stable statin dose will be determined by the Investigator using his/her medical judgment and available sources, including the participant's self-reported history of lipid-modifying therapy for at least 8 weeks prior to Screening (Visit 1); and

For any participant not taking statin therapy due to statin intolerance, including those participants taking bempedoic acid or fibrate monotherapy, written confirmation will be required of both the participant and the Investigator stating that the participant was statin intolerant, aware of the benefit of statins to reduce the risk of a MACE, and aware that many other patients who are unable to tolerate a statin were actually able to tolerate a different statin or dose.

Note: Statin intolerance will be defined as intolerance due to an adverse safety effect that started or increased during statin therapy and resolved or improved when statin therapy was discontinued, resulting in an inability to tolerate either 1) two or more statins at any dose, or 2) one statin at any dose and either an unwillingness to attempt a second statin or advice by a physician not to attempt a second statin.

- Ezetimibe for at least 8 weeks with or without maximally tolerated statin prior to Screening (Visit 1);
- Bempedoic acid for at least 8 weeks in combination with a maximally tolerated statin prior to Screening (Visit 1); and/or
- A PCSK9-targeted therapy alone or in combination with other lipid-modifying therapy for at least 4 stable doses prior to Screening (Visit 1).

Note: At least 70% of the participants enrolled into this study must be taking HIS. Documentation in the electronic case report form (eCRF) of the reason why a participant is unable to take HIS is required. HIS include the following: atorvastatin 40 and 80 mg and rosuvastatin 20 and 40 mg.

- 5. Have a fasting serum LDL-C at Screening (Visit 1) as follows:
  - Have a fasting serum LDL-C  $\geq$ 55 mg/dL ( $\geq$ 1.4 mmol/L) to <100 mg/dL (<2.6 mmol/L) OR non-HDL-C  $\geq$ 85 mg/dL ( $\geq$ 2.2 mmol/L) to <130 mg/dL (<3.4 mmol/L) with at least 1 of the following risk enhancers:
    - Recent MI (>3 and <12 months prior to Randomization [Visit 2]);
    - Type 2 diabetes mellitus;

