#### 4.2 Exclusion Criteria

Participants who meet any of the following criteria will be excluded from participation in the study:

- 1. Have current or any previous history of New York Heart Association class III or IV HF or left ventricular ejection fraction <30%;
- 2. Have been hospitalized for HF within 5 years prior to Screening (Visit 1);
- 3. Have had any of the following clinical events within 3 months prior to Screening (Visit 1):
  - o Non-fatal MI;
  - Non-fatal stroke;
  - o Non-elective coronary revascularization; and/or
  - O Hospitalization for unstable angina and/or chest pain.
- 4. Have uncontrolled severe hypertension, defined as either systolic blood pressure ≥160 mmHg or diastolic blood pressure ≥100 mmHg prior to Randomization (Visit 2) taken as the average of triplicate measurements. One triplicate retest will be allowed during the same visit, at which point if the retest result is no longer exclusionary, the participant may be randomized;
- 5. Have a formal diagnosis of homozygous FH;
- 6. Have active liver disease, defined as any known current infectious, neoplastic, or metabolic pathology of the liver; unexplained elevations in alanine aminotransferase (ALT) or aspartate aminotransferase (AST) >3 × upper limit of normal (ULN); or total bilirubin >2 × ULN at Screening (Visit 1);
  - Note: An abnormal ALT, AST, or total bilirubin must be confirmed by a repeat abnormal measurement at least 1 week apart.
- 7. Have HbA1c ≥10.0% (≥0.100 hemoglobin fraction) or a fasting glucose ≥270 mg/dL (≥15.0 mmol/L) at Screening (Visit 1);
- 8. Have thyroid-stimulating hormone  $\geq 1.5 \times ULN$  at Screening (Visit 1);
- 9. Have creatine kinase (CK)  $>3 \times$  ULN at Screening (Visit 1);
- 10. Have a history of a malignancy that required surgery (excluding local and wide local excision), radiation therapy, and/or systemic therapy during the 3 years prior to Randomization (Visit 2);
- 11. Have a known history of alcohol and/or drug abuse within 5 years prior to Randomization (Visit 2);

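### The laboratory criteria for new-onset diabetes carry no Baseline condition, so, if programmed as written, the event-of-special-interest count mixes prevalent with new diabetes

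*SAP*

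**What the plan says.** New-onset diabetes mellitus (NODM) is part of one event of special interest (ESI), next to worsening of glycaemic control. SAP 3.5.2 and Protocol 8.2.5 define it identically: "NODM is defined by 1 or more of the following criteria, based upon information from AE, medication, and laboratory data".

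The four criteria are:
- an adverse event, worded as "AE indicating new type 1 or type 2 diabetes";
- start of an anti-diabetes drug, with the diagnosis confirmed by blinded external experts;
- "HbA1c ≥6.5% (≥ 0.065 hemoglobin fraction); and/or";
- "Two consecutive values of fasting plasma glucose that are" at or above 126 mg/dL.

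Worsening of glycaemic control is an HbA1c rise from Baseline of more than 0.5% and/or a new drug or "increase in current antidiabetic therapy in a participant with a Baseline HbA1c" of at least 6.5%.

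Protocol 4.1, inclusion criterion 5, lists "Type 2 diabetes mellitus" among the risk enhancers for entry. Protocol 4.2, exclusion criterion 7, removes only those who "Have HbA1c ≥10.0% (≥0.100 hemoglobin fraction) or a fasting glucose ≥270 mg/dL" or above. SAP 3.5.2 then reports each ESI as a count and percentage by treatment group, with a listing. The Safety Population is everyone who took a dose.

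**The concern.** The HbA1c and glucose criteria do not ask for absence of a diabetes history, absence of anti-diabetes treatment, a Baseline value below the threshold, or any change from Baseline. Expert confirmation is attached to the medication criterion alone. A participant who enters with treated type 2 diabetes and stays at the same HbA1c above 6.5% therefore satisfies the definition at the first post-Baseline sample.

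Protocol 8.2.5 says that ESIs are followed whether or not they were reported as adverse events, from the adverse event and laboratory databases. The laboratory criteria are thus working criteria. At stake is whether the NODM percentage in each arm describes new disease or mostly the diabetes that participants brought into the trial.

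**Working it through.** **No figure to reproduce.** Neither document states an expected NODM rate, a prevalence of diabetes, or a power for this event.

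**Is the rule restricted elsewhere?**
- Protocol 8.2.5.3 speaks of diabetes newly diagnosed during the study, but refers back to 8.2.5 for how it is identified.
- Protocol 9.2.2.1 and the later part of SAP 3.5.2 say that NODM cases are summarised by system organ class, severity and relationship to study drug. They add no at-risk condition.
- In the same SAP section, liver and CK abnormalities are split by normal or abnormal Baseline, and the antihypertensive-medication event by prior diagnosis and Baseline treatment. NODM has no such split.

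**Are the laboratory criteria testable early and often?** HbA1c and fasting glucose are in both the full and the limited chemistry panel (Protocol Appendix B). One of these panels is drawn at every visit from Screening to Day 365 (Appendix A).

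**Size of the effect, under assumptions.** Let d be the share with diabetes at Baseline, c the share of those who meet a criterion after Baseline (the same in both arms), and p the true new-onset rate in the rest. Then

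rate as written = d × c + (1 − d) × p.

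Example with d = 0.20, c = 0.90, and p = 4% on placebo and 6% on obicetrapib:
- placebo: 0.20 × 0.90 + 0.80 × 0.04 = 0.180 + 0.032 = 21.2%;
- obicetrapib: 0.180 + 0.80 × 0.06 = 0.180 + 0.048 = 22.8%;
- ratio 22.8 / 21.2 = 1.08, against a true 6 / 4 = 1.50;
- prevalent share of the obicetrapib cases: 0.180 / 0.228 = 79%.

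Other assumed values (p is placebo / obicetrapib):

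| d | c | p | True ratio | Rate as written | Ratio as written |
|---|---|---|---|---|---|
| 10% | 0.7 | 8% / 12% | 1.50 | 14.2% / 17.8% | 1.25 |
| 10% | 0.9 | 4% / 6% | 1.50 | 12.6% / 14.4% | 1.14 |
| 20% | 0.7 | 5% / 7% | 1.40 | 18.0% / 19.6% | 1.09 |
| 30% | 0.9 | 4% / 6% | 1.50 | 29.8% / 31.2% | 1.05 |
| 40% | 0.7 | 5% / 7% | 1.40 | 31.0% / 32.2% | 1.04 |
| 40% | 0.9 | 4% / 6% | 1.50 | 38.4% / 39.6% | 1.03 |

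With d from 10% to 40%, c of 0.7 or 0.9, and rates of 4% / 6% or 8% / 12%, prevalent cases make up 39% to 91% of the obicetrapib NODM cases. The risk difference shrinks by the factor (1 − d).

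**What does not change.** The expected excess of true cases is the same. In the worked example with 1,600 on obicetrapib it is 1,600 × 1.6% = 25.6 as written, and 1,280 × 2.0% = 25.6 in the restricted set. Only its visibility against the background falls.

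**Dependence on equal c.** If c differs by arm, the ratio as written is a weighted average of c(obicetrapib) / c(placebo) and the true new-onset ratio. With equal c the first term is 1, so the pull is toward 1. With unequal c it is toward the ratio of the two c values, which need not be 1.

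**The case against.** The strongest reply is that the intent is plain. The term is new-onset, the adverse event criterion says new, Protocol 8.2.5.3 speaks of new diagnosis, and a separate worsening category exists for participants with a high Baseline HbA1c. A sensible programmer would exclude known diabetes. This stands as evidence of intent, and it makes the harm conditional on literal programming. It does not supply the rule: history, medication, HbA1c and glucose each give a different at-risk set, and neither document chooses.

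A reader might infer three stronger things that the documents do not support.

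- *A glycaemic safety signal would be lost.* SAP 3.4.3 compares HbA1c, HOMA-IR and glucose at Day 365 between arms by ANCOVA, and SAP 3.5.3 summarises laboratory changes from Baseline. The NODM tables by severity and relationship rest on attributes of adverse event records. Protocol 8.2 keeps conditions present at Screening out of those records unless they change. The exposed output is mainly the ESI overview count.
- *The safety board's review would be swamped.* The board does see ESIs about every six months, but its methods are in a charter outside these documents.
- *A treated participant with diabetes and Baseline HbA1c below 6.5% who deteriorates fits no category.* Under the rule as written, an HbA1c that reaches 6.5% would still count as NODM. The gap needs an informal restriction of NODM and also one reading of an ambiguous sentence. If the Baseline HbA1c qualifier governs only the medication limb, the rise of more than 0.5% captures this participant.

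It is also fair that SAP 3.5 plans no inference on safety endpoints, so test statistics or power for this count would describe an analysis that nobody will run.

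**Conclusion.** The definition is wrong as written: its two laboratory criteria classify stable, known diabetes as new-onset, and no other section of either document corrects this. If it is programmed literally, the ESI overview count and percentage mix prevalent with new cases.

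The direction, toward a ratio of 1, holds if prevalent cases qualify at similar rates in both arms. The size cannot be fixed from the documents. A true ratio of 1.4 to 1.5 falling to about 1.03 to 1.25 is an illustration that rests on assumed values for prevalence, qualifying share and new-onset risk. The problem is confined to this count. It does not reach the other glycaemic analyses in the same way, and no formal test depends on it. It deserves correction because, where safety is only described, the displayed percentages are the evidence.

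**What to change.** Before unblinding, change how the event is counted:

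1. Define the NODM at-risk set, as both numerator and denominator, as Safety Population participants with no diabetes history, no anti-diabetes medication and HbA1c below 6.5% at Baseline.
2. Count only post-Baseline laboratory values toward the HbA1c criterion and the two-consecutive-glucose criterion. A single high Baseline glucose then removes nobody from the set.
3. Define all remaining participants as having diabetes at Baseline and report worsening of glycaemic control in that complementary set. Every participant then falls in exactly one set.
4. State whether the Baseline HbA1c qualifier in the worsening rule governs both limbs or only the medication limb. If it governs both, members of this set with Baseline HbA1c below 6.5% could never count, and the SAP should address that openly.
5. Align the wording of Protocol 8.2.5, or list the change in SAP section 6, which now records three changes and not this one.

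The cost is SAP wording, a derived Baseline flag, and the Protocol alignment or section 6 entry. Medical history, medications, HbA1c and fasting glucose are already collected, so no new data are needed.
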